**22. Frequency of DSM reviews:** The PI meets about monthly will research staff to monitor study progress. The informed consent process, fidelity to inclusion and exclusion criteria, and the integrity of the overall data and safety monitoring plan are also reviewed in these meetings. Problems identified during monitoring will lead to an immediate corrective plan and possible reporting to the IRB and NIDA Project Officer, depending on the problem.

**23. Content of DSM Report.** Reports will include data that inform progress of the study, including baseline demographics, adverse events data, and accrual status. In addition, a database of AEs and SAEs will be maintained by the study coordinator. About once per month, in the research team meetings, all adverse events will be reviewed that occurred over the prior month, as well as over the course of the trial. In addition, the local IRB maintains records of AEs and SAEs. All SAEs are reviewed and records sent to NIDA and the IRB per their standard policies.

A DSM report will be sent to NIDA on an annual basis, at the same time as the Annual Non-Competing renewal. The categories include: 1) description of any non-administrative changes in the study protocol; 2) baseline sociodemographic characteristics of new enrollees; 3) any new quality assurance problems or changes; 4) any new regulatory issues; 5) summary of all AEs/SAEs and any related changes to the consent form or study protocol; 6) any significant protocol violations and deviations, and any corrective actions undertaken to eliminate future occurrences; and 7) summary of the literature review conducted in the prior year to assess for any newly reported risks associated with IGD interventions.

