Both parents may participate and will complete the parental assessments (est. 2 hours), and both (when available) can participate in the therapy, consistent with how family therapy is typically provided. Both parents and children will complete a therapy satisfaction form post treatment. Children and parents will receive \$30 in gift cards for completing the baseline assessment and the 4 week follow-up and \$50 in gift cards for the post-treatment and 24 week follow-up interviews (up to \$160/family member).

Family members may complete their follow-up measures through the survey function of REDCap in advance of their in-person meetings. When the research assistant calls to schedule the follow-ups, participants will be given the option of receiving the survey link through e-mail, receiving a paper copy of the assessments by mail, or completing the measures when they arrive for their in-person meeting. The week 4 assessment can be completed in its entirety by the participant at home through REDCap or the mail, unless the participant prefers an in-person meeting. Study visits may be completed over the phone if needed.

Parents will provide:

- basic demographics, including age, SES, gender, and education of parents and child, and indices of the child's school functioning: grades, tardiness, absences and disciplinary issues

- modified Treatment Service Review (TSR; McLellan et al., 1992) questionnaire about histories and current treatments received (of the child). Additional questions specific to treatment for video game addiction treatment will be administered at all time points.
- Parents will provide data about their own psychological symptoms (Brief Symptom Inventory [BSI]; Derogatis, 1992)
- emotional regulation (Difficulties in Emotion Regulation Scale [DERS]; Gratz & Roemer, 2004).
- Parents' perceptions of their child's gaming will be evaluated by a revised VGDS (Rehbein et al., 2015), which includes items about types and locations of all gaming devices in the home and frequencies with which they monitor their child's gaming behaviors.
- a semi-structured clinical interview using DSM-5 criteria (SCID; Petry et al., 2014), assessed over past year and past 2 months at BL and past 2 months at other time points.
- Parents will complete a TimeLine Follow-Back (TLFB; Sobell & Sobell, 1990) of the child's gaming, time spent watching others play online (e.g., YouTube, Twitch), and sleep

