- Child's participation in extracurricular activities will be assessed via a checklist from the Michigan Study of Adolescent Life Transitions study (MSALT; Eccles & Barber, 1999)
- A modified version of the Parenting Style Index (Steinberg, Lamborn, Dornbusch, & Darling, 1992), which includes a checklist of types and frequencies with which they use tangible rewards (money, goods) and verbally praise their child
- the Brief Family Assessment Measure (BFAM; Skinner et al., 1995, 2000)
- Perceived Social Support Scale (PSSS; Procidano & Heller, 1983).
- Child Behavior Checklist (CBCL; Achenbach, 2001), an index of child competencies and internalizing and externalizing symptoms
- Conners' Parent Rating Scale—Revised (CPRS-R; Conners, 2008), a measure of emotional and behavioral problems, including ADHD.
- Parents will assess their own quality of life via the Quality of Life Inventory (QoL: Frisch et al., 1992)
- quality of life of their child using the caregiver version of the Questionnaire for Measuring Health-related Quality of Life in Adolescents (KINDL-R; Ravens-Sieberer, 2000).
- AUDIT (Saunders et al., 1993) a brief questionnaire about their own alcohol use
- DUDIT (Hildebrant, 2105) a brief questionnaire about their own substance use
- parent version of the Behavior Rating Inventory of Executive Functioning (BRIEF; Guy et al., 2004) will evaluate executive function of their child
- the Social Responsiveness Scale, a brief autism spectrum screen (Constantino et al., 2003)
- the Barrett Impulsiveness Scale (BIS-11), a measure of their own impulsivity (Patton, Stanford, & Barratt, 1995)

Children will complete parallel instruments:

- VGDS (Rehbein et al., 2015), including items about types and locations of gaming devices in the home,
- DSM-5 based clinical interview for IGD (SCID; Petry et al., 2014);
- TLFB of days and durations of play, time spent watching others play online (e.g., YouTube, Twitch), and sleep
- participation in extracurricular activities via the MSALT assessment (Eccles & Barber, 1999) and school functioning.
- A modified version of the Parenting Style Index (Steinberg, Lamborn, Dornbusch, & Darling, 1992), which includes a checklist of types and frequencies of tangible rewards (money, goods) and verbal praise provided by parents will be administered
- indices of social support and family communication including the PSSS
- BFAM
- Teen Addiction Severity Index (Kaminer et al., 1999);

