- Social Phobia and Anxiety Inventory for Children (Beidel et al., 1995);
- Center for Epidemiological Studies-Depressed Mood scale (Radloff, 1977);
- Pittsburgh Sleep Quality Index (Buysse et al., 1989).
- the Youth Self-Report (Achenbach, 1991) of emotional and behavioral problems,

- DERS (Gratz & Roemer, 2004),
- quality of life KINDL-adolescent version (Ravens-Sieberer, 2000)
- the adolescent version of the Barrett Impulsiveness Scale (BIS-11), a measure of their own impulsivity (Patton, Stanford, & Barratt, 1995)

**Randomization.** After baseline, families will be randomized via a computerized algorithm (Stout et al., 1994) to groups below. Groups will be stratified by child age ( $\leq 15$  or over), sex, and parents participating (one vs. both).

**A. Referral for care.** Therapists will explain that gaming problems often co-occur with other mental health problems, and effective treatment for the latter may reduce gaming as well. Therapists will refer parents to local support groups such as Department of Mental Health and Addiction Services and National Association for Mental Illness support groups. Adolescents will be referred for appropriate services as well, e.g., depression, social anxiety, ADHD, or substance use depending on co-occurring problems.

**B. Referral plus Behavioral therapy** will consist of referral for other services plus 6 family sessions (adapted from Petry, unpublished; Appendix). In Session 1, therapists will review baseline information, refer for other services, and orient participants to treatment. They will remind parents that although they cannot prevent playing entirely, they can better understand why and when their child is playing and alter their reactions toward it, which may decrease the extent of play and problems. Therapists will describe methods to re-arrange the home to better monitor and be less conducive toward playing; this may include altering locations of or removing some (or all) gaming devices from the home. Therapists will review a tracking form and instruct parents how to and benefits of closely monitoring their child's playing. Children will be asked to keep their own log as well.

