Session 2 will focus on goal setting for gaming, ranging from 0 to  $\leq 12$  hrs/week (Council on Communications and Media, 2013). It will begin with a review of past weeks' logs. Therapists will troubleshoot difficulties with monitoring and concordance of child and parent logs. They will review patterns of play to identify high-risk times and days, and circumstances that may have impacted playing. Therapists will outline norms related to game playing and media use in general to guide selection and maintenance of reasonable goals.

In session 3, therapists will review logs and how actual gaming aligned or not with goals. Therapists will also introduce the concept of replacing high-risk game playing times with alternate activities. The parent, and child, will review a list of recreational activities the child does or may enjoy. At least 2-3 activities will be identified to occur at high risk gaming times in the upcoming week. Over the next week, participants will continue recording gaming and times in which parents encouraged alternate activities and the child's responses.

Session 4 will review goals in light of increasing alternate activities, and therapists will introduce the concept of rewarding non-game playing behaviors this session. They will outline possible rewards, and parents will develop a concrete plan to reward their child for not playing during high-risk times in the next week.

Session 5 will continue discussions of rewards for non-gaming playing behaviors. Therapists will review rewards provided and encourage continued rewarding of non-game playing and other positive behaviors in the future. The session will focus on communication styles, and the parent and child will role play assertive communication skills, especially as they relate to game playing.

Session 6 will review progress and discuss long-term goals. Therapists will remind parents to continue to monitor play, offer alternatives to play, and reward non-gaming behaviors to prevent relapse. The therapist will help parents to problem solve any barriers to successful implementation of the behavior plan.

Six sessions will be scheduled about once per week over 8 weeks, allowing for missed or re-scheduled sessions. The goal will be to complete 6 sessions over 8 weeks; no reschedules will occur after week 12. Sessions may be completed over the phone if needed.

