Aim 1: To evaluate the feasibility and acceptability of this intervention, the proportion assigned to the intervention who complete all 6 sessions will be examined, as will parent and child ratings of satisfaction.

Aim 2: To examine the effect size of the intervention on reducing game playing days and durations of play, we will analyze TLFB data collected at each assessment period, with the greater report of parent or child used for each day. Hierachial linear models (HLM; Gibbons et al., 1993; Raudenbush & Byrk, 2002) will compare differences between groups over time. HLM is specifically designed for repeated measures designs with missing data, allowing for intra-subject serial correlation and unequal variance and covariance structures over time by incorporating available trend data for each individual with information on the group from which the subject is drawn. Maximum likelihood estimation enables analyses to be performed for the full trial without having to drop subjects with incomplete data, and both continuous and dichotomous variables can be analyzed. The model will include factors representing group, time, and their interaction, along with any important covariates.

We will also compare proportions of subjects by group who are no longer gaming problematically, i.e., child reports no current DSM-5 IGD criteria and/or <5 criteria, and parent confirms no more problems for the most conservative approach. Logistic regressions will include important demographics and baseline indices of distress and severity of problems in Step 1. Step 2 will add treatment to determine if it adds unique variance in predicting outcomes after controlling for baseline indices. See section 4 above for power analysis.

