Exploratory aims are to evaluate potential mechanisms of actions of the intervention including: changes in number and location of gaming devices in the home, frequency of monitoring child's game playing (via self reports in both groups, and confirmed by completed logs in Group B), child's participation in alternate activities (ACC), and parental rewarding of child behaviors and family communications (PSSS, BFAM scores). Following recommendations of Morgenstern and Longabaugh (2000) for assessing mediation, Model 1 examines whether the treatments engender differential outcomes on gaming indices (i.e., Aim 2 above). Model 2 will test if potential mediators change differentially over time by condition. For these analyses, a composite indicator for each construct will be utilized (e.g., summary scores of number/location of gaming devices, monitoring frequencies, ACC, PSS and BFAM scores). Model 3 will examine partial correlations between post-treatment scores on these indices and gaming outcomes, after controlling for baseline scores. If these three models show significant effects, the final model will assess associations between these variables and gaming outcomes. Step 1 of this model will include baseline scores of the potential mediator(s). In step 2, treatment group will be entered, and in step 3, post-treatment scores of the mediator(s) will be included, and resulting predictive power of treatment condition examined. If treatment is no longer significant and the post-treatment mediation term is significant, criteria for full mediation are met. Although we do not expect to find full mediation with this sample size, potential mediators with medium or higher effect sizes in Models 2-3 will be considered for future evaluation and inclusion in this intervention, if main effects of treatment are noted (Aim 2).

We will also assess effect sizes on secondary outcomes, e.g., substance use, psychosocial functioning and symptoms, sleep, and quality of life. HLM, outlined above, will compare groups over time on these indices.

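### The monitoring mediator can change how its own gaming outcome is measured, so Model 3 and the final mediation model can be biased for monitoring in either direction

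*Combined protocol and SAP*

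**What the plan says.** **Mediator.** The assessment list under Approach gives parents a revised VGDS with items on gaming devices and on the "frequencies with which they monitor their child's gaming behaviors". The child's entry reads "VGDS (Rehbein et al., 2015), including items about types and locations of gaming devices in the home" and names no monitoring item. The exploratory aims (Data analysis, and item 10 of the Detailed Data and Safety Monitoring Plan) describe the mediator as "frequency of monitoring child's game playing (via self reports in both groups, and confirmed by completed logs in Group B").

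**Outcome.** Aim 2 analyses TLFB gaming data "with the greater report of parent or child used for each day". Model 1 of the mediation sequence is the Aim 2 comparison. No separate gaming outcome is defined for Model 3 or the final model.

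**Models and their use.** Model 3 is specified as "Model 3 will examine partial correlations between post-treatment scores on these indices and gaming outcomes, after controlling for baseline scores". Then: "If these three models show significant effects, the final model will assess associations between these variables and gaming outcomes". A mediator with at least a medium effect in Models 2 and 3 is considered for later evaluation and inclusion, provided that Aim 2 shows a treatment effect.

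**What differs by arm.** In the behavioural therapy arm parents are taught close tracking of play. For the child, "Children will be asked to keep their own log as well". In session 2, "Therapists will troubleshoot difficulties with monitoring and concordance of child and parent logs". The referral arm has none of this.

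**The concern.** Monitoring is how a parent learns how much the child plays. The parent who supplies the monitoring score can also set the recorded value on any day when the parent's report is the larger. The mediator can therefore act on recorded gaming by two routes: by changing play, which is the mechanism of interest, and by changing what is reported. Model 3 cannot separate them.

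The intervention is designed to change monitoring after baseline and in one arm only, so adjusting for baseline scores does not remove the second route. The plan has no single-reporter version of the mediation models, and its parent-child concordance analysis is not linked to them.

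At stake is the choice of content for the next version of the intervention. Monitoring is a core component. A biased Model 3 could make a useful component look weak, or an inert one look promising.

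**Working it through.** The plan gives no power or effect figure for the mediation models, so there is none to reproduce. Its stated power (d = 0.65, 30 per group) concerns the group comparison and is not used here. The documents do not say how completely children report or parents detect play. **All reporting inputs below are assumptions**, as is the 28-day TLFB window.

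**Step 1. One day, by hand.** Let true play be T, the child's report c × T, and the parent's report (0.70 + s × M) × T, where M is monitoring in SD units and s the gain in detection per SD. The recorded value is max(child, parent).

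- c = 0.70, s = 0.10, M = 0: max(0.70, 0.70) × T = 0.70 T.
- c = 0.70, s = 0.10, M = +1: max(0.70, 0.80) × T = 0.80 T. Recorded play is 0.80/0.70 = 1.14 times as high for the same true play.
- c = 1.00, s = 0.10, M = +1: max(1.00, 0.80) × T = 1.00 T. Detection changes nothing.

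The detection route therefore needs children to under-report.

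**Step 2. Many families.** The same formulas were simulated for 20,000 families and 28 days, with reporting noise and a true correlation of monitoring with play of -0.30. Mean play and noise are also assumed, and the results move by several hundredths with them.

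| Child reports | Detection gain per SD | Correlation with greater-of score |
|---|---|---|
| 60-80% | none | -0.29 to -0.30 |
| 60-80% | 5 points | -0.15 to -0.25 |
| 60-80% | 10 points | -0.01 to -0.19 |
| 60-80% | 15 points | +0.09 to -0.14 |
| 100% | with a gain | -0.26 to -0.29 |

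**Step 3. Model 3 at the trial's size.** This used 60 families, the daily maximum, and a partial correlation adjusted for baseline monitoring and baseline gaming, with 400 runs per scenario. With 60 - 2 - 2 = 56 degrees of freedom, the two-sided 5% critical value is 2.00/√(56 + 2.00²) = 0.26.

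| Assumed reporting | Greater-of r | Chance of a significant negative r |
|---|---|---|
| True effect, undistorted outcome | about -0.30 | 0.61 to 0.66 |
| True effect, detection rises, child reports all | -0.29 | essentially as above |
| True effect, detection rises moderately, child reports 70% | -0.23 | 0.44 |
| True effect, detection rises strongly, child reports 70% | -0.12 | 0.16 |
| True effect, detection rises, child reports 40% | +0.16 to +0.36 | 0 |
| True effect, monitoring cuts parental error | -0.37 to -0.52 | 0.86 to 0.99 |
| No true effect, monitoring cuts parental error | -0.10 to -0.31 | 0.11 to 0.70 |

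The last two rows arise because the larger of two noisy reports is pulled upward by noise. If monitoring makes the parent's report less noisy, the recorded maximum falls without any change in play. Full child reporting does not protect against this route: those runs gave -0.42 to -0.52.

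**Step 4. Child's report alone.** In the strong-detection and parental-error runs, the correlation with the child's TLFB stayed at -0.29 to -0.30 with a true effect, and within 0.02 of zero without one. This is partly by construction, because child reporting was held independent of monitoring. In a separate large-sample run with the child at 70%, letting child reporting rise 5 points per SD of monitoring moved the child-only correlation to about -0.08.

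**The case against.** The strongest reply is that nothing in the documents shows that children under-report or that monitoring raises detection, so both size and direction come from the assumptions. That stands. A reader might infer that closer monitoring necessarily raises recorded gaming and that Model 3 will discard a working mechanism. The documents do not support this: the bias may run the other way, or be negligible.

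Several textual objections also hold in part:

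- A reader might say that monitoring rests on the parent's word alone. The plan has logs confirm it in Group B. That check covers one arm, and it confirms the mediator, not the outcome.
- The child's VGDS entry is worded as including device items, so the absence of a child monitoring item is inferred from silence.
- A reader might extend the point to every mediator as parent-reported. Devices, rewards, PSSS and BFAM are completed by both reporters, so that extension fails.
- Aim 2 also covers IGD status, which the daily maximum does not score. The point concerns TLFB days and durations.

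Finally, the aim is exploratory, full mediation is not expected, and qualifying mediators are only considered for inclusion. Sampling error is also large. For r = -0.30 with 60 families and two covariates, z = -0.310 and SE = 1/√55 = 0.135, so -0.310 ± 0.265 back-transforms to about -0.52 to -0.05. This lowers the priority. It does not remove the point, because the bias is systematic and a larger trial with the same scoring would keep it.

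**Conclusion.** The concern holds in a limited form. Monitoring and the greater-of outcome are not measured independently, and neither baseline adjustment, the Group B logs nor the concordance analysis corrects this. Model 3 and the final model can therefore mislead for monitoring.

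Under the assumptions shown, a true partial correlation near -0.30 can appear as anything from +0.36 (strong detection gain, child reporting 40%) to -0.52 (monitoring cuts parental error). If children report fully, added detection has almost no effect. With no true effect, a significant negative result appeared in 11% to 70% of parental-error runs. These figures show what is possible. They do not estimate the bias in this trial, which depends on reporting behaviour that the documents do not give.

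This is worth fixing in the SAP because it bears on a carry-forward decision and costs little. It does not call the Aim 2 scoring rule into question.

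**What to change.** In the exploratory aims (Data analysis, and item 10 of the Detailed Data and Safety Monitoring Plan):

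1. In Model 3 and the final model, analyse parent-reported monitoring against the child's own TLFB report and present it beside the greater-of result.
2. Report the parent-child TLFB discrepancy by arm and by level of monitoring at each TLFB assessment, so that a shift in reporting is visible.
3. State that the carry-forward decision for monitoring will not rest on the greater-of result alone.
4. Keep the greater-of rule for Aim 2.

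The mirror-image step, relating child-reported mediators to the parent's TLFB, is not advised, because that outcome is the most exposed to changes in detection. In a run with a 10-point detection gain and a true correlation of -0.30, it gave +0.13, against about -0.10 for greater-of.

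**Cost.** SAP wording and a few extra model runs; both TLFBs are already collected. A one-reporter outcome is noisier. Child reporting may itself change under monitoring, particularly in the arm where children keep logs and concordance is worked on. If it shifts while the parent's does not, the child-only result could be the worse of the two. It is a check, not a bias-free answer.
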